## **8.6 Data Management**

Data will be collected on CRFs and transferred to an electronic database following a double entry protocol. Entry fields will include pre specified data ranges and distributions will be regularly checked for the presence of outlier or extreme values.

# **9 POTENTIAL RISKS AND BENEFITS**

## **9.1 Potential Risks**

### **9.1.1 Risks related to the procedures**

#### **Venipuncture**

Blood samples will be obtained by venipuncture of an antecubital vein to determine the levels of CLA NO2-cLA, nitrite, and other inflammatory biomarkers.

Risks: The risks of venipuncture are minimal. The possible risks include bruising and/or infection at the site of the venipuncture and vasovagal episodes experienced by the blood donors.

Pressure will be applied to the venipuncture site to prevent bruising. Aseptic technique will be used to prevent infection. Blood will be obtained while the donors are in a seated position and medical and nursing personnel will be available at the study sites to treat and manage vasovagal episodes.

Benefits: There are no direct benefits to the participant

### **Pulmonary Function Testing (spirometry)**

Spirometry will be performed to determine the participants' pulmonary function.

Risks: The risks of spirometry are minimal. The possible risks include precipitation of bronchospasm and light-headedness from repeated blowing attempts. Medical and nursing personnel and medications will be available at the study sites to treat and manage bronchospasm. Inhalation of a short-acting beta-2 adrenergic agonist (such as albuterol) will be used to assess reversibility at some visits. The possible risks of inhaled beta-2 adrenergic agonists include tachycardia and hand tremors. These side effects are non-life threatening and are short-lived.

Benefits: Spirometry with assessment of reversibility to a short-acting beta-2 adrenergic agonist will be used to determine if the participants meet the inclusion criteria for this study; it will also serve as a secondary outcome for the study.

The potential benefits justify the potential risks.

### **Methacholine Inhalation Challenge**

Methacholine challenge will be used to assess airway hyper-responsiveness at baseline and after treatment. This measurement is being made primarily as function of safety to ensure that CLA + NOx do not potentially enhance airway hyperresponsiveness in these patients.

Risks: The major risk of methacholine challenge is the induction of severe bronchoconstriction. As a precaution, participants will not undergo methacholine challenge if their FEV1 is less than 50% of predicted or 1.0 liter. Medical and nursing personnel, medications and equipment will be available at the study sites to treat and manage any bronchoconstriction episodes.

Benefits: There are no direct benefits to the participant. This procedure is considered necessary for the protocol as a safety measure for this pilot, POC study.

### **Bronchoscopy**

Risk from bronchoscopy are hemoptysis, epistaxis, and local discomfort, fever and a sore throat. Sedation will be given as part of the bronchoscopy and the medications used for this can cause hypotension, lightheadedness or dizziness; these side effects are somewhat common but very short in duration. Appropriate monitoring equipment and medications will be used to promptly identify and manage complications if they occur. Bronchoscopy may cause coughing and occasionally gagging. Fever or chills may occur, especially following a lavage. Chest pain from a collapse of a small segment of the lung (atelectasis) may occur. Some people experience temporary vomiting, soreness of the nose and throat Mild to moderate cough can be

observed for 24 hours after the procedure. The greatest risk of bronchoscopy is transient worsening of asthma. This rarely occurs in mild-moderate asthmatic subjects (<5%), but can occur in up to 25% of severe asthma subjects. Every precaution is taken to prevent this, including giving 40-60 mg of prednisone to severe asthmatics prior to discharge. The subject's asthma may worsen during or after the procedure. In those rare cases, we may ask them to spend the night in the Clinical Translational Research Center (CTRC). There has been only one death (worldwide) associated with a research bronchoscopy so this is very, very rare event. Overall, research bronchoscopy in adult asthmatics is a safe and well-tolerated procedure (49).  
Protection against Risk: First during the bronchoscopy, patients are placed on supplemental oxygen and monitored continuously with oxygen saturation monitor as well as electrocardiogram. Due to the potential of increased risk of complications with asthmatic subjects undergoing a bronchoscopy, subjects are pretreated with beta-agonists. The topical anesthesia and sedation dosages are monitored and limits set and adhered to closely. Research bronchoscopies will only be done on subjects with a post bronchodilator FEV1 predicted of ≥50%.

### **Urine Collection**

Urine will be collected to assess overnight urine cortisol, to perform pregnancy tests at specified visits, and for future exploratory assessments of urine biomarkers.

Risks: There are no risks associated with urine collection.

Benefits: This test will be used to determine PGD2 metabolite levels and isoprostanes.

### **Tongue Scrape**

The subject's tongue will be gently scraped to collect cell samples. Following collection, the samples will be brought to the PI's lab and used to develop cell cultures for research purposes.

Risks: The main risk associated with this procedure is minor discomfort and/or irritation of the tongue.

Benefits: There are no direct benefits to the participant.

## **9.1.2 Study Specific Risks**

### **Treatment with CLA**

CLA isomers have been designated as “generally regarded as safe by the Food and Drug Administration”, based on human and animal data that show that there is no indication of

significant CLA-related adverse effects. Human studies have shown that continuous administration of CLA in the dose range proposed in this study, is well tolerated and does not result in serious adverse effects. Doses of up to 10 g / day for short periods have resulted in no adverse events in healthy subjects

([www.fda.gov/downloads/food/ingredientspackaginglabeling/gras/noticeinventory/ucm408896.pdf](http://www.fda.gov/downloads/food/ingredientspackaginglabeling/gras/noticeinventory/ucm408896.pdf)).

### **Nitrite**

[name], a collaborator in this study, has previously held an IND for sodium nitrite (IND # 70,411) for cardiovascular applications and currently has an approved IND for the use of sodium nitrite for lung transplant recipients (IND # 111,643). The cardiovascular IND involved the administration of sodium nitrite to 69 normal volunteers in 4 phase I-II clinical trials without observed adverse effects. He has also treated 11 subjects with sickle cell disease on this IND without observed adverse effects. The low doses of nitrite used in these investigational treatment regimens – less than 75 mg or 25% of the dose (300mg) used in the emergency treatment of cyanide poisoning – do not produce methemoglobin levels greater than 3% and have not been associated with clinically significant hypotension. There have been no adverse events noted in the 80 treated normal human volunteers and patients with sickle cell disease (50-52). In another study by Gladwin et al., 18 healthy adults received an infusion of sodium nitrite totaling 75 mg (15 minutes each x 2 infusions). This was associated with a 7 mm Hg decrease in mean arterial pressure, a peak methemoglobin of less 3% and no other significant effects(51). Note this dose is 3.75 times the dose we plan to use in this trial.

In an open-label three-way crossover study, 9 healthy adult subjects received two single high dose oral sodium nitrite aqueous solutions (0.12 and 0.06 mmol NaNO2/mmol Hb, equivalent to 290-380 mg and 140-190 mg sodium nitrite, respectively, depending on the total body hemoglobin level of the person) and one intravenous sodium nitrite dose (0.12 mmol NaNO2/mmol Hb)(53). Mild headache occurred in 44-55% of subjects and was the most frequent complaint during each treatment session, which the authors ascribed to the sodium nitrite, not methemoglobinemia, as the percentage of methemoglobinemia stayed below clinically toxic levels (<15%). By report, up to 22% experienced nausea, which subsided within half an hour(53). The pharmacokinetic analysis of this study indicated similar bioavailability of oral and IV delivery of nitrite, as well as similar side effect and safety profiles.

## **Nitrate**

For nitrate, some toxicity studies suggest a positive association with risk of non-Hodgkin lymphoma, gastric and colon cancers with years of exposure. However, these were mostly studies with weak study design and limited strength of evidence. Other case-control studies and cohort studies, which provide stronger evidence, have found no increased risk of human cancer with increasing nitrate intake from diet or drinking water after multivariate adjustment. Taking all studies together, the CONTAM panel (Contaminants in the Food Chain) of the European Food Safety Authority (EFSA) reports evidence does not suggest that nitrate intake from diet or drinking water is associated with increased cancer risk. In addition, there is no clear evidence of an effect of nitrate or nitrite on non-cancer human health effects(43).

In the current study, we will use much lower doses of nitrite and nitrate than used safely in any of these studies. Our sodium nitrite dose of 20 mg per day is <30% of the dose used on the cardiovascular IND and <7% of the dose used for cyanide poisoning. Our sodium nitrate of 1,000 mg represents a nitrate ion dose (i.e. 744 mg) that is less than the nitrate ion dose (i.e. 933 mg) associated with 1,488 mg of potassium nitrate used by Webb and colleagues(39). To summarize, We anticipate the following symptoms by organ system and likely frequency of risk during the 6 week treatment in this study:

### **Gastrointestinal**

- Common: none
- Frequent: none
- Rare: nausea, abdominal pain and vomiting

### **Hematologic**

- Common: none
- Frequent: none
- Rare: methemoglobinemia

### **Cardiovascular**

- Common: none
- Frequent: none
- Rare: flushing, tachycardia, hypotension

### **Neurologic**

- Common: none
- Frequent: none
- Rare: headache, dizziness, seizure, coma

## Respiratory

- Common: none
- Frequent: none
- Rare: tachypnea, dyspnea, cyanosis

## **Prednisone Burst**

Oral prednisone may cause nausea, vomiting, loss of appetite, heartburn, trouble sleeping, and rise in blood sugar or increased sweating.

## **9.2 Plan for Patient Safety**

Study population: To enhance safety we will exclude patients with: a) history of ICU admission/intubation due to asthma; b) More than three systemic corticosteroid requiring asthma exacerbations in the past year; c) an asthma exacerbation requiring systemic corticosteroids within 30 days preceding study enrollment; d) systemic steroid dependent asthma and e) FEV1 < 50 % predicted.

## **9.3 Routine Safety Monitoring**

Potential risk mitigation will be achieved through monitoring including study visits and telephone contacts every 2 weeks will help identify participants who experience worsening of control or have an asthma exacerbation during the study. Between in-person study visits, participants will be contacted by telephone by the clinic coordinator to ensure appropriate compliance with the study protocol, to answer any questions, and to ensure their asthma is not worsening, as assessed by the participant. We will follow criteria established by Asthmanet, which proposes an algorithm based on measures of asthma control and healthcare utilization, to determine whether a participant's asthma is worsening or he/she is experiencing an asthma exacerbation (REF). The PI or investigator will determine whether the participant is showing signs of treatment failure using criteria identified below. If it is determined that the participant fulfills criteria for treatment failure or an asthma exacerbation, they will be advised to visit the study center within 24 hours for evaluation and initiation of treatment as specified herein. In the absence of these criteria, arrangements will be made for the participant to have telephone contact or return to the clinic at the next regularly scheduled interval.

If, between phone contacts or in-person visits, an asthma exacerbation occurs, the participant should be evaluated at the nearest medical emergency facility as quickly as possible.

Participants will be instructed to call the coordinator or the investigator within 24-48h of

receiving care for an exacerbation. The PI may determine whether a participant needs to be seen at the study center following an exacerbation.

Treatment failure (defined for safety purposes) or significant worsening of asthma status will be defined as the identification of the occurrence of one or more of the following while enrolled in the study (these parameters do not apply to the 72 hour post-bronchoscopy period when these may be an expected adverse event following the procedure):

1. An increase in PRN albuterol/levalbuterol use of  $\geq 6$  puffs (1 neb equals 4 puffs) per 24 hours over baseline use for 48 hours;
2. Scheduled or unscheduled visit to the study center for worsening of asthma symptoms with a change in pre-bronchodilator  $FEV_1 \leq 80\%$  of the baseline on 2 consecutive measurements;
3. Additional inhaled (doubling or more) of baseline dosing or oral corticosteroids for more than 3 consecutive days, or more than one parenteral corticosteroid dose due to asthma;
4. Need for emergency treatment at a medical facility that is related to asthma, or results in hospitalization for an acute asthma exacerbation;
5. Participant refusal to continue study drugs because of lack of satisfaction with treatment;  
or
6. An increase of the ACQ score of 1.5 from pre-treatment, or an absolute score of 2.5.

Participants will be provided with action plans to communicate with the study investigators if any of these events occur. The study investigator will determine whether the participant should follow up with a visit after patient has received care for an exacerbation in a healthcare facility.

## **10 DATA AND SAFETY MONITORING PLAN**

### **10.1 Data Safety and Monitoring Board**

A Data Safety and Monitoring Board (DSMB) will be created to review this study. The DSMB will contain at least 3 members or experts in pulmonary diseases. None of the DSMB members will be affiliated with this study or have a conflict of interest.

### **10.2 Data Safety and Monitoring Plan**

The DSMB will meet at periodic intervals during the course of the study. The DSMB will be expected to convene as needed, but not less than every 6 months to review the progression of the study including subject enrollment, protocol compliance, and adverse event reports. The DSMB will conduct interim monitoring of accumulating data from research activities to assure

the continue safety of human subjects, relevance and appropriateness of the study, and the integrity of research data.

The study Principal Investigator has primary responsibility for the oversight of the data and safety monitoring. The Investigator will review subject safety data as it is generated. The Investigator, sub-investigators, and the research staff will meet on a four week interval to re-evaluate study goals, subject recruitment, data coding and retention, documentation and identification of adverse events, complaints and confidentiality of subjects. There will be an evaluation of the progress of the research study, including assessments of data quality, time lines, participant recruitment, accrual, and retention. The Investigator will also review the outcome and adverse event data to determine whether there is any change to the anticipated benefit-to-risk ratio of study participation and whether the study should continue as originally designed or should it be re-evaluated and changed.

The study investigators will evaluate all adverse events (AEs). All subjects who have AEs, whether considered associated with the use of the study medication or not, must be monitored to determine the outcome. The clinical course of the AE will be followed up according to accepted standards of medical practice, even after the end of the period of observation, until a satisfactory explanation is found or the Principal Investigator considers it medically justifiable to terminate follow-up.

### **10.3 Reporting of Serious Adverse Events and Unanticipated Problems**

#### **Investigator's Reporting Requirements to the IND Sponsor**

Investigator will report all serious, unexpected, and study-related adverse events to the IND Sponsor within 24 hours. The investigator will then submit a detailed written report to the IND Sponsor. The DSMB, all investigators, and IRB will also be promptly notified in accordance with the respective policies and procedures.

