***Additional IND Reporting Requirements***

The IND Sponsor will report any clinically important increase in the rate of a serious suspected adverse reaction over that listed in the protocol. A baseline incidence rate may not always be available, but when one is available, a clinically important increase from that rate will be reported. The decision about when to report is a matter of judgment based on a variety of factors including the study population, the nature and seriousness of the reaction, and the magnitude of the observed increase in the rate.

The IND Sponsor will submit annually an Annual Report to the FDA. The Annual Report will include a written summary of the status of all clinical studies being conducted under the IND

application. The IND Sponsor will work with the reporting investigators to prepare a detailed written summary of serious, unexpected, and treatment related adverse events, and will compare, and contrast the event with prior events. The detailed written summary will also be provided to the DSMB and the IRB.

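### The only stated duty to report to the IND Sponsor covers serious events that are also unexpected and study-related, so the Sponsor need not receive the serious listed reactions that its own rate-increase rule depends on

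*Combined protocol and SAP*

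**What the plan says.** Section 10.3, under the investigator's requirements to the IND Sponsor, states: "Investigator will report all serious, unexpected, and study-related adverse events to the IND Sponsor within 24 hours". A detailed written report follows, and the DSMB, the other investigators and the IRB are notified of the same events.

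Under the additional IND requirements, the same section gives the Sponsor a duty of its own: "The IND Sponsor will report any clinically important increase in the rate of a serious suspected adverse reaction over that listed in the protocol". It adds a qualification: "A baseline incidence rate may not always be available, but when one is available, a clinically important increase from that rate will be reported".

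Section 9.1.2 introduces its list of reactions with "We anticipate the following symptoms by organ system and likely frequency of risk during the 6 week treatment in this study". The entries include:
- "Rare: methemoglobinemia"
- "Rare: flushing, tachycardia, hypotension"
- "Rare: headache, dizziness, seizure, coma"

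Every entry in the list is graded Rare. No incidence figure is attached to any of them.

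**The concern.** The two halves of Section 10.3 do not fit together. The investigator's rule screens out expected events before they leave the site. The Sponsor's rate rule concerns reactions whose rate is already listed in the protocol, which are the expected ones. A Sponsor working only from the data flow as written could not count the cases that it is asked to monitor.

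The screen also puts two judgements, expectedness and relatedness, with the site before the Sponsor sees the case. A serious event that the site calls unrelated need not arrive either, so the Sponsor has no stated chance to take a different view.

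Section 8.4 notes that CLA and NOx have not been given together for asthma. Experience with the combination is therefore thin, and each serious case carries weight.

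**Working it through.** The plan states no figure on this point, so there is none to reproduce. The check compares the passages and then gives a small illustration.

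**1. Are the three conditions cumulative?** The sentence in Section 10.3 could in principle name three separate classes of event. That is unlikely. The paragraph on the Sponsor's responsibilities speaks of events that are both serious and unexpected, and the annual summary repeats the three-part phrase with *treatment related* as its third term. The conditions apply together.

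**2. What falls outside them?** Section 9.1.2 lists gastrointestinal 3, hematologic 1, cardiovascular 3, neurologic 4 and respiratory 3: 3 + 1 + 3 + 4 + 3 = 14 reactions, all introduced as anticipated. Some, such as headache or flushing, would seldom be serious. Methemoglobinemia, hypotension, seizure and coma could be. On a plain reading none of the 14 is unexpected.

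**3. What does the rate rule need?** It needs counts of serious suspected reactions that the protocol already lists. The investigator's rule obliges the site to send none of these, whatever the true rate.

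**4. Is there another route to the Sponsor?**

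| Place | What it covers | Stated transfer to the Sponsor |
|---|---|---|
| 10.3, annual written summary | Same three-part condition | Yes, but only for events already screened |
| 10.2, investigator and team review | Safety data as they arise; meetings every four weeks | None |
| 10.2, DSMB | Adverse event reports, at least every 6 months and when needed | None |

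No row supplies the missing cases.

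**5. Illustration with the planned n = 12 (Section 8.1).** The documents give no rate for serious listed reactions, so the rates p below are assumptions. The chance of at least one case is 1 − (1 − p)^12:

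| Assumed p | Chance of at least one case in 12 |
|---|---|
| 0.1% | 1.2% |
| 1% | 11.4% |
| 5% | 46.0% |
| 10% | 71.8% |

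One case is 1/12 = 8.3% (exact 95% interval 0.2% to 38.5%). With no case in 12, the one-sided 95% upper limit is 1 − 0.05^(1/12) = 22.1%. One case that is not passed on therefore changes the observed rate materially. The interval also shows how little 12 participants can say about a rate.

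**The case against.** The strongest reply is that the rule sets a minimum. It does not say that only these events are reported, and it does not forbid sending others. *Unexpected* is undefined, and the list in Section 9.1.2 gives symptoms without severity. An investigator could treat a coma or a serious seizure as unexpected because of its severity. The study is single-center, and the documents do not show how close the Sponsor is to the study team, so an informal route may exist. All of this stands, and it limits the claim to the data flow as written. It does not remove the mismatch, because a safety rule should not depend on an unstated definition or an unwritten route.

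A second reply is that full reporting would not make the rate rule work. With only *Rare* in the protocol there is no numeric baseline, and Section 10.3 concedes that one may be missing and leaves the decision to judgement. This also stands. The screen is one of two limits on the rule.

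A reader might infer more than the documents support:

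- **That asthma hospitalizations after bronchoscopy are exempt from serious-event reporting.** Section 9.3 says "these parameters do not apply to the 72 hour post-bronchoscopy period when these may be an expected adverse event following the procedure", but that clause sits inside the definition of treatment failure and says only that such events *may* be expected. Section 7.4 gives hospitalization as its example of a post-procedure complication or serious adverse event. The first bronchoscopy also precedes study drug, so an event then cannot be a suspected drug reaction.
- **That nobody looks at these events between six-monthly DSMB meetings.** Section 10.2 provides for investigator review as data arise, team meetings every four weeks and DSMB meetings when needed. What is missing is a stated transfer to the Sponsor.
- **That a given number of participants would finish treatment between DSMB reviews.** The documents give no accrual rate and no rule on sequential enrolment.
- **That the Sponsor holds the safety data from the other nitrite INDs.** Section 9.1.2 attributes those INDs to a collaborator and does not identify that person as the Sponsor.

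**Conclusion.** The concern holds as a mismatch within Section 10.3. The investigator's rule does not require serious listed reactions, or serious events judged unrelated, to reach the IND Sponsor, while the Sponsor's rate rule needs the serious listed reactions. No other section fills the gap.

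The conclusion assumes that *unexpected* has its plain meaning, so that a reaction listed as anticipated is expected, and that no unwritten route exists. It does not depend on the sample size or on any assumed rate. It does not show that events would go unseen at the site or by the DSMB, nor that the screen is the only reason the rate rule is weak.

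This should be fixed before enrolment continues, but it does not put the efficacy analysis in doubt.

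**What to change.** In Section 10.3, have the investigator report every serious adverse event to the IND Sponsor within 24 hours, whether or not it is expected and whatever its judged relationship to the study. Keep unexpectedness and association with the drug as the Sponsor's criteria for the 7-day and 15-day reports, where the protocol already places them.

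Three companion edits would complete the change:
- Define *serious* and *unexpected*, and say whether a listed reaction of greater severity counts as unexpected.
- Widen the annual written summary to match the new rule.
- State what baseline, if any, the rate rule uses, since *Rare* alone gives none. The sentence that introduces the list refers to 6 weeks of treatment, while Sections 5.2 and 6 describe 8. These passages must be reconciled so that any rate refers to a known exposure period.

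The cost is protocol wording and a few extra serious-event forms in about 12 participants. Treatment, visits and efficacy analyses are unaffected.
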